NCT03728140

Study Protocol & Statistical Analysis

12/01/2019

Objective:

A total of 335 couples participated in this study, which was performed between January 2018 and December 2019 at the Reproductive Medicine Department, Jinan Central Hospital Affiliated to Shandong University, and Reproductive Medicine Center, Gansu Provincial Maternity and Child-care Hospital. The couples underwent ICSI/IVF treatment and their high quality embryos were randomized to embryo transfer using either fresh or self-spent medium with informed consents and ethics approvals.

Design:

Patients met the following criteria were included: (i) ≤ 35 years old; (ii) regular menstrual cycles; (iii) baseline follicle stimulating hormone (FSH) <12 IU/L; (iv) infertility with simple tubal or/and male factors; (v) did not experience more than two prior failed ET cycles; (vi) at least two good-quality Day 3 embryo or one good-quality Day 5 blastocyst for ET. Exclusion criteria were as follows: (i) uterine abnormalities, such as adenomyosis, endometriosis and endometrial polyps; (ii) ovarian abnormalities, such as low ovarian response and polycystic ovary syndrome (PCOS); (iii) endometrial thickness <7 mm on transfer day.

Methods:***Ovarian stimulation and IVF/ICSI procedure***

Controlled ovarian hyperstimulation was carried out with uninterrupted injection of recombinant FSH (Gonal-F; Merck Serono; Switzerland) following pituitary down-regulation by GnRHa. When the dominant follicles measured ≥ 18 mm in diameter, human chorionic gonadotrophin (hCG, Lizhu Inc, China) or recombinant hCG (Ovidrel, Merck Sereno, Switzerland) was administered, and oocyte retrieval was performed approximately 36.5 h later. Sperms were prepared using density gradient centrifugation and swim-up techniques before fertilization, and IVF/ICSI procedures were applied 4–6 h after oocyte retrieval. Fertilization was assessed by checking the appearance of two pronuclei 16–18 h later.

Embryo culture

After fertilization, embryos were cultured one by one in G1TM-PLUS medium drops (Vitrolife, V.Frölunda, Sweden) containing human serum albumin and gentamicin covered with OVOILTM (Vitrolife, V.Frölunda, Sweden) in the culture dish until Day 3, G2TM-PLUS medium was sequential used from Day 3 to Day 6 if the embryos need to blastocyst culture. All mediums for embryo culture were pre-equilibrated at 37°C and 6% CO₂ before use.

Cleavage stage embryos were morphologically classified according to the number and shape of blastomeres, the percentage of fragmentation as well as multinucleation on Day 3, as following: Grade 1, no or <5% fragmentation with at least six equal-sized blastomeres and no multinucleation; Grade 2, <20% fragmentation with slightly unequal-sized blastomeres and no evidence of multinucleation; Grade 3, 20%–50% fragmentation with obviously unequal-sized cells; and Grade 4, >50% damage or severely unequal-sized cells or visible multinucleation. Blastocysts were classified according to development stage (staging 1-5) and morphology of inner cell mass (Grading A-C) and trophectoderm (Grading A-C).

Embryo transfer

Two Day 3 fresh cleavage stage embryos scored better than grade 2 or single Day 5 fresh blastocyst stage embryo scored better than 4BB was selected for intrauterine transfer. The selected embryos were pre-transferred into a 500 µl pre-equilibrated fresh culture medium (G1TM-PLUS or G2TM-PLUS) awaiting ET. In the test group, the stretched thin Pasteur pipettes were used to absorb the self-spent droplets under the oil, and the droplets were transferred at least three times in a new dish to remove the oil floating on the surface. Then, the selected embryos were transferred to the combined droplet for catheter loading. Correspondingly, the embryos of the control group were loaded directly in the pre-equilibrated fresh culture medium. Luteal support by progesterone administration was provided to the patients after transfer.

Outcome Measures

Chemical pregnancy was confirmed by detecting serum β -hCG level 14 days after embryo transfer, and clinical pregnancy was defined as presence of at least one gestational sac identified by ultrasound 5 weeks after transfer. Biochemical pregnancy rate was defined as the number of early pregnancy losses divided by the total number of positive serum β -hCG. Clinical pregnancy rate was defined as the number of clinical pregnancies divided by the number of transfer cycles. Implantation rate was calculated as the number of gestational sacs divided by the number of embryos transferred. Clinical abortion rate was defined as the number of clinical pregnancy losses before 28 weeks of gestation divided by the total number of clinical pregnancies. Live birth rate was defined as a ratio between healthy living newborns and embryo transfer cycles.

Statistical Analysis:

Data were analyzed using student's t-test and chi-square test. $P < .05$ was considered statistically significant.

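### Clinical pregnancy and live birth are counted per transfer cycle, with allocation timing unstated and no as-allocated analysis set, so any prognosis-related loss between allocation and transfer could bias the comparison

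*Combined protocol and SAP*

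**What the plan says.** Two definitions under Outcome Measures set the denominator: "Clinical pregnancy rate was defined as the number of clinical pregnancies divided by the number of transfer cycles" and "Live birth rate was defined as a ratio between healthy living newborns and embryo transfer cycles".

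Under Design, one exclusion criterion is "endometrial thickness <7 mm on transfer day", and one inclusion criterion is "at least two good-quality Day 3 embryo or one good-quality Day 5 blastocyst for ET". The Embryo transfer section gives its own selection rule: "Two Day 3 fresh cleavage stage embryos scored better than grade 2 or single Day 5 fresh blastocyst stage embryo scored better than 4BB". The plan does not define good quality in terms of those scores.

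Allocation is described only under Objective: "their high quality embryos were randomized to embryo transfer using either fresh or self-spent medium". No day, method or ratio is given, and no concealment or blinding is described. The same section reports that "A total of 335 couples participated in this study". It does not say whether these couples were enrolled, randomised or transferred, or how they divide between the arms.

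The Statistical Analysis section consists of a t-test, a chi-square test and a 0.05 threshold. It names no analysis population and gives no rule for a couple allocated but not transferred, or allocated to one medium and loaded in the other.

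**The concern.** A rate per transfer cycle drops from both numerator and denominator any couple who was allocated but had no transfer. Randomisation makes the arms comparable at allocation, not at transfer. If couples can leave in between, if the two arms lose different numbers or kinds of couple, and if those lost differ in prognosis, part of the per-transfer difference reflects who remained. The chi-square test cannot separate that part from an effect of the medium.

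The plan leaves room for this because one criterion is checked on transfer day and the order of that check and allocation is not given. After allocation, the arms also differ in handling. Only in the test group is it said that "the stretched thin Pasteur pipettes were used to absorb the self-spent droplets under the oil", followed by repeated moves to clear the oil. No as-allocated rule covers a couple for whom that step does not succeed.

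Live birth has a second problem. Its numerator counts newborns, so a two-embryo transfer that yields twins adds two to the numerator and one to the denominator. The result is not a proportion of cycles or couples, which is what a chi-square test compares.

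**Working it through.** The plan states no expected rate, effect size, drop-out or number per arm, so it has no figure to reproduce. What follows is a sensitivity calculation on stated assumptions.

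**Inputs**
- From the documents: 335 couples; threshold 0.05.
- Assumed: 168 test and 167 control couples, all randomised; a two-sided test; a true pregnancy rate p of 50% in both arms had every couple been transferred; loss in the test arm only, of a fraction d; and a rate r among those lost, had they been transferred.

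**Formulas**
- Pregnancies left in the test arm = 168 × p − 168 × d × r.
- Per-transfer rate = that number / (168 × (1 − d)).
- By-couple rate = that number / 168.
- Control rate = 83.5 / 167 = 50%.
- The false-positive rate is the rejection probability of the pooled two-proportion z test, equivalent to chi-square without continuity correction.

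| d | r | Per-transfer test rate | Bias (points) | False-positive rate |
|---|---|---|---|---|
| 2% | 0 | 84 / 164.64 = 51.0% | +1.0 | 0.054 |
| 5% | 0 | 84 / 159.6 = 52.6% | +2.6 | 0.076 |
| 10% | 0 | 84 / 151.2 = 55.6% | +5.6 | 0.167 |
| 5% | 25% | 81.9 / 159.6 = 51.3% | +1.3 | 0.056 |
| 10% | 25% | 79.8 / 151.2 = 52.8% | +2.8 | 0.078 |
| any | 50% | 50% | 0 | 0.05 |

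**One false-positive rate in full (d = 5%, r = 0)**
- Pooled rate = (84 + 83.5) / (159.6 + 167) = 0.513.
- Null standard error = √(0.513 × 0.487 × (1/159.6 + 1/167)) = 0.0553. The unpooled value is also 0.0553.
- Critical difference = 1.96 × 0.0553 = 0.108.
- With a shift of 0.0263, the upper tail is about 0.069 and the lower about 0.007, giving 0.076.

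**Range over p from 40% to 60%**
- 5% lost, r = 0: +2.1 to +3.2 points, false-positive rate 0.067 to 0.090.
- 10% lost, r = 0: +4.4 to +6.7 points, 0.126 to 0.233.
- 10% lost, those lost at half the base rate: +2.2 to +3.3 points, 0.069 to 0.093.

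Equal loss in both arms, with equal prognosis among those lost, gives no bias and 0.05.

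**The same cases by couple randomised**
- With r = 0 the test rate is 84 / 168 = 50%, the difference is 0 and the false-positive rate is 0.05.
- With r = 25% and 10% lost it is 79.8 / 168 = 47.5%. This is lower than control because couples without a transfer did not conceive in that cycle.

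**The case against.** The strongest reply is that the order of events probably makes the two denominators nearly the same. Thickness and embryo quality are both listed as eligibility criteria. What was randomised is described as embryos already of high quality, which fits allocation after grading, and grading of fresh Day 3 or Day 5 embryos falls at or near transfer. The media differ only at catheter loading, so the allocated medium cannot have changed thickness or grade beforehand. This is a fair reading, and it is why post-allocation loss cannot be asserted. It remains an inference, because grading before allocation does not place the endometrial check before allocation.

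A reader might infer that a failed droplet recovery removes test-arm couples from the denominator. The text does not support this. The selected embryos are already waiting in fresh medium, and nothing mentions failed recovery or cancelled transfers. If such embryos were loaded in fresh medium, a transfer cycle would still occur and the couple would still be counted. That would be crossover, which creates no bias when the medium has no effect. What remains is the need to say in which arm such a couple is analysed.

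The worst-case figures also combine two conditions that the documents do not join. Thin endometrium may relate to prognosis but is not caused by the arm. Droplet failure would be specific to one arm, but nothing ties it to a lower chance of conception.

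**Conclusion.** The point holds as a conditional one. Both main rates use transfer cycles, one exclusion is assessed on transfer day, allocation timing is not given, and no as-allocated set is named. The comparison therefore keeps the protection of randomisation only if no couple was lost between allocation and transfer, and the reader cannot check whether that is so.

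Two stronger readings go too far. One is that the transfer-day criteria did remove randomised couples, which no section shows. The other is that unequal loss by itself biases the comparison. It does so only when those lost differ in prognosis; with equal prognosis the difference is zero however unequal the loss.

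The size is +2.6 points at 5% loss and +5.6 points at 10% loss, with false-positive rates of about 7.6% and 17%. These are worst-case values. They rest on the assumed 50% rate, a near-even split of 335 couples, loss in one arm only, and no chance of conception among those lost. Halving the prognosis instead of removing it brings the bias down to +1.3 and +2.8 points. The change is worth making because it costs almost nothing and removes the doubt.

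**What to change.** 1. Define the main clinical pregnancy rate as couples with a clinical pregnancy divided by couples randomised, and the main live birth rate as couples with at least one live birth divided by couples randomised. Changing only the live birth denominator would not be enough, since the numerator would still count newborns.
2. Analyse every couple in the arm allocated. Count couples without a transfer as no pregnancy and no live birth, and keep test-arm couples loaded in fresh medium in the test arm.
3. Keep the per-transfer rates as secondary descriptions.
4. Confirm that the couple was the unit allocated, since the text names embryos. Report when allocation was actually opened relative to the thickness check and embryo selection. The study is described in the past tense, so this can be reported but no longer set as a rule.
5. Report, by arm, the numbers randomised and the numbers randomised but not transferred.

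The cost is a change of wording and a few counts, with no extra couples. The stated rates may be slightly lower. An arm that lost couples for reasons unrelated to prognosis will show a lower by-couple rate, and the secondary per-transfer rate and the counts let the reader see this. If no couple was lost, the clinical pregnancy comparison does not change (given one transfer cycle per couple and no change of arm).

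### Implantation rate is counted per embryo, but Day 3 couples contribute two embryos to one transfer, so an embryo-level chi-square gives too small a P value if their outcomes are positively correlated

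*Combined protocol and SAP*

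**What the plan says.** Three parts of the combined protocol and SAP bear on this.

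- **Outcome Measures** makes the embryo the denominator: "Implantation rate was calculated as the number of gestational sacs divided by the number of embryos transferred". Pregnancy is counted on a different unit: "Clinical pregnancy rate was defined as the number of clinical pregnancies divided by the number of transfer cycles".
- **Embryo transfer** sets the number of embryos per transfer at two or one: "Two Day 3 fresh cleavage stage embryos scored better than grade 2 or single Day 5 fresh blastocyst stage embryo". In the test group "the selected embryos were transferred to the combined droplet for catheter loading". For the comparator, "Correspondingly, the embryos of the control group were loaded directly in the pre-equilibrated fresh culture medium". Both embryos of a Day 3 transfer therefore receive the same medium.
- **Statistical Analysis** is two sentences long. The data are analysed with Student's "t-test and chi-square test. $P < .05$ was considered statistically significant". It does not link tests to outcomes, and it names no unit of analysis, no robust or clustered variance, and no per-couple version of implantation rate.

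The Objective section says of the couples that "their high quality embryos were randomized to embryo transfer using either fresh or self-spent medium". Read literally this makes the embryo the randomised unit, but the loading procedure keeps the embryos of one transfer in one arm.

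**The concern.** A chi-square test on sacs over embryos counts each embryo as a separate independent observation. Two Day 3 embryos from one couple share their parents, the transfer, the endometrium and the medium under test, so their outcomes may well move together. Because both sit in the same arm, positive correlation adds to the variance of the difference between arms. The chi-square ignores that extra variance.

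The consequence is a P value that is too small and a two-sided type I error above the nominal level, with the excess split about equally between the two directions. The estimated rates and their difference do not change. Clinical pregnancy rate, with one observation per transfer cycle, does not have this problem.

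**Working it through.** The plan has no sample-size or power figure to reproduce, so the check starts from the nominal 5% level and asks what an embryo-level chi-square delivers.

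**Inputs from the documents.** The Objective section says "A total of 335 couples participated in this study". Cluster size is two embryos (Day 3) or one (Day 5). The significance level is 0.05.

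**Assumptions, not in the documents.** 168 and 167 couples per arm; one transfer per couple; Day 3 share *d* of 25%, 50% or 100%, equal in both arms; within-pair correlation (ICC) from 0 to 0.5, with −0.1 as a check; the same implantation rate at both stages, 40% unless stated.

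**Design effect.** Per couple there are on average 1 + *d* embryos, of which 2*d* belong to pairs. Each paired embryo has its variance contribution multiplied by 1 + ICC. Hence

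DE = 1 + 2*d* × ICC / (1 + *d*).

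**True two-sided type I error of the uncorrected test.** α = 2 × [1 − Φ(1.96 / √DE)].

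Example, *d* = 0.5 and ICC = 0.3: DE = 1 + (2 × 0.5 × 0.3)/1.5 = 1.20; 1.96/√1.20 = 1.789; α = 7.4%. The 335 × 1.5 ≈ 502 embryos carry the information of about 419.

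| ICC | *d* = 25% | *d* = 50% | *d* = 100% |
|---|---|---|---|
| 0 | 5.0% | 5.0% | 5.0% |
| 0.1 | 5.5% | 5.8% | 6.2% |
| 0.3 | 6.4% | 7.4% | 8.6% |
| 0.5 | 7.4% | 9.0% | 11.0% |

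In one direction the error is half of this: 2.7% to 5.5% for ICC 0.1 to 0.5, against a nominal 2.5%. At ICC −0.1 the test is conservative, with an error of 3.9% to 4.5%.

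**Simulation check.** Pearson chi-square on embryos, 60,000 runs per setting:

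| *d*, ICC | Two-sided error | Share favouring the test arm |
|---|---|---|
| 25%, 0.1 | 5.55% | 2.69% |
| 50%, 0.3 | 7.43% | 3.71% |
| 100%, 0.5 | 10.79% | 5.49% |

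At ICC 0 the error was 4.9% to 5.1%. A couple-level ratio test on the same data held 5.0% to 5.3%. Runs of 200,000 at rates of 30%, 40% and 50% gave 7.3% to 7.4% for the second setting and 10.7% to 11.1% for the third.

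**Effect on a reported P value.** A chi-square P of 0.04 has z = 2.054. Dividing by √DE gives P = 0.044 at DE 1.04, 0.061 at DE 1.20 and 0.094 at DE 1.50. The largest chi-square P that stays below 0.05 after adjustment has z = 1.96 × √DE, that is P of about 0.046, 0.032 and 0.016 respectively.

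**Precision.** With a 40% rate and about 251 embryos per arm, the naive 95% half-width for the difference is 1.96 × √(0.24 × 2/251) = 8.6 points. At DE 1.20 it is 8.6 × √1.20 = 9.4 points. The plan does not propose an interval, so this applies only if one is reported.

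**The case against.** The strongest reply is that the size of the problem rests on quantities the documents do not give and on an inferred test.

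- **The test is not assigned.** The plan does not say that chi-square is used for implantation rate, and a t-test on per-couple proportions would respect the pairing. This stands as a caveat. But the outcome is defined as a pooled ratio, not per couple, and chi-square is the only listed test suited to it. On either reading the unit has to be stated.
- **A continuity correction may apply.** The plan does not say. With the Yates correction and a 40% rate, the simulated error is about 4.4% to 5.2% at ICC 0.1, about 6% at a 50% Day 3 share and ICC 0.3, and about 7.4% at 100% and ICC 0.3. So at low correlation the corrected test can stay below 5%. This qualifies the size. It is not a remedy: the corrected test starts at about 4.0% at ICC 0 and rises with the correlation in the same way.
- **The correlation is unknown.** It could be zero or even negative, in which case there is no inflation. The 11% figure needs every couple at Day 3 and an ICC of 0.5, an extreme because the plan provides for Day 5 transfers. This is fair, and the conclusion is conditional for that reason.
- **The reach is limited.** Clusters hold at most two embryos, the estimate is unbiased, no outcome is named as primary, and clinical pregnancy rate covers related ground with the right unit. These points keep the issue below a critical one. They do not make the implantation P value valid.

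**Conclusion.** The concern holds. Read naturally, the plan tests a per-embryo proportion as if paired embryos were independent, and nothing else in the document corrects for this. If the within-pair correlation is positive, the P value for implantation rate is too small. For an uncorrected chi-square, with ICC 0.1 to 0.5 and Day 3 share 25% to 100%, the true two-sided error is 5.5% to 11.0%; it is lower with a continuity correction, and there is no excess at ICC 0. These ranges rest on assumed values for the correlation, the Day 3 share, the allocation and the implantation rate. The inflation is modest at low correlation, but in the middle of the range it is enough to carry a P of 0.04 across the plan's only decision threshold. It should be fixed. It affects implantation rate and not clinical pregnancy rate.

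**What to change.** Add one or two sentences to Statistical Analysis. State that the couple is the unit of analysis for implantation rate. Keep sacs over embryos as the estimate, and obtain its P value, and any confidence interval, by one of these:

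- GEE with an independence working correlation and robust variance clustered on couple; or
- a ratio estimator with couple-level variance or a bootstrap that resamples couples.

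The independence structure should be named. With clusters of one and two embryos, an exchangeable structure reweights couples and no longer returns the pooled ratio that the plan defines. In one simulated dataset (*d* = 50%, ICC 0.3, assumed rates 35% at Day 3 and 55% at Day 5) the pooled difference was −10.5 points, independence GEE gave −10.5 and exchangeable GEE gave −9.8.

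The cost is a few lines of code. No new data are needed, because the method uses only sacs and embryos per couple, which the outcome already requires. When the correlation is positive, the P value is slightly larger and any interval slightly wider; when it is zero, almost nothing changes.

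### The two pregnancy-loss rates are divided by counts formed after randomisation, and live birth counts newborns rather than couples, so a chi-square on any of them needs a limited reading and a per-couple companion

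*Combined protocol and SAP*

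**What the plan says.** The Objective section states that "their high quality embryos were randomized to embryo transfer using either fresh or self-spent medium". Outcome Measures then places the hCG test 14 days after transfer and the ultrasound that defines clinical pregnancy 5 weeks after transfer.

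The outcomes use three kinds of ratio:

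- Loss among pregnancies. The rate called biochemical pregnancy is "the number of early pregnancy losses divided by the total number of positive serum" β-hCG results. The clinical abortion rate is "the number of clinical pregnancy losses before 28 weeks of gestation divided by the total number of clinical pregnancies".
- A yes/no result per transfer cycle. "Clinical pregnancy rate was defined as the number of clinical pregnancies divided by the number of transfer cycles".
- A count of babies per transfer cycle. "Live birth rate was defined as a ratio between healthy living newborns and embryo transfer cycles". The Embryo transfer section allows "Two Day 3 fresh cleavage stage embryos scored better than grade 2 or single Day 5 fresh blastocyst stage embryo", so some transfers can lead to twins.

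The whole analysis text is "Data were analyzed using student's t-test and chi-square test", with P < .05 as the threshold. It does not assign a test to any outcome, name a primary outcome, or mark the loss rates as descriptive.

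**The concern.** Randomisation makes the couples in the two arms comparable. It does not make those who later have a positive hCG test, or a gestational sac, comparable. Pregnancy is itself an outcome of this trial, so the medium may change who enters the two loss denominators.

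The distortion needs two things together: the medium changes which couples become pregnant, and the pregnancies it adds or removes carry a different risk of loss from the rest. A P-value on loss per pregnancy then mixes an effect on loss with a change in who is at risk. It could be reported as showing that self-spent medium does, or does not, raise pregnancy loss, and randomisation would not support either statement.

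The natural safeguard is live birth, which carries the net effect. As defined, however, it adds up newborns. A twin delivery counts twice, so the ratio is not a proportion of couples and a chi-square for proportions does not fit it.

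**Working it through.** The plan gives no event rates and no power calculation, so it has no figure of its own to reproduce.

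**Inputs.** From the documents: 335 couples, alpha .05, chi-square, and the definitions above. Assumed: 168 test and 167 control couples, an uncorrected two-sided test, control pregnancy 50% with 10% of these lost (so 45% live birth), one generic loss rate, all live births healthy, and no loss after 28 weeks.

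**1. Order of events.** Randomised transfer, hCG at day 14, ultrasound at week 5, loss before 28 weeks. Both loss denominators form after allocation and after exposure to the medium.

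**2. Size on assumed rates.** On test, the control pregnancies recur with unchanged loss. A further fraction e of couples becomes pregnant, and a fraction q of these extra pregnancies is lost.

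- Loss per pregnancy on test = (0.05 + e·q)/(0.50 + e), against 0.10
- Loss per couple on test = 0.05 + e·q, against 0.05
- Live birth on test = 0.45 + e·(1 − q), against 0.45

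For e = 0.10, q = 0.5: 0.10/0.60 = 16.7%, 10.0% and 50.0%. Rejection percentages from 400,000 simulated trials per row:

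| e | q | Loss per pregnancy on test | Test per pregnancy | Test per couple | Live birth test |
|---|---|---|---|---|---|
| 0.05 | 0.1 | 10.0% | 4.9 | 5.3 | 12.7 |
| 0.05 | 0.3 | 11.8% | 6.6 | 8.8 | 9.5 |
| 0.05 | 0.5 | 13.6% | 11.2 | 15.1 | 7.2 |
| 0.10 | 0.1 | 10.0% | 5.0 | 6.6 | 37.4 |
| 0.10 | 0.3 | 13.3% | 10.2 | 19.3 | 24.6 |
| 0.10 | 0.5 | 16.7% | 25.4 | 40.6 | 14.8 |

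The rows with q = 0.1 show the second condition at work: more couples are pregnant, but with the same loss risk the per-pregnancy test stays at about 5%.

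**3. Equal pregnancy rates are not a safeguard.** Assume 40% of couples are pregnant under either medium (12% lost), 10% only under fresh medium (12% lost) and 10% only under self-spent medium (40% lost). Pregnancy is 50% in both arms. Loss per pregnancy is 12.0% on control and (0.40×0.12 + 0.10×0.40)/0.50 = 17.6% on test. The chi-square rejects in 17% of trials.

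**4. A per-couple loss test is not a cure.** Two cases give the same per-couple loss, 10.0% against 5.0%, a difference of 5.0 points (95% CI −0.6 to 10.6):

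- A, 10 points of extra pregnancies with half lost: live birth 50% against 45%, difference +5.0 (−5.7 to 15.7).
- B, no extra pregnancies, 20% against 10% lost: live birth 40% against 45%, difference −5.0 (−15.6 to 5.6).

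The half-width in A is 1.96 × √(0.50×0.50/168 + 0.45×0.55/167) = 10.7 points. The intervals overlap widely, and the observed live birth difference has the wrong sign in about 18% of trials in each case.

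**5. Chi-square on newborns.** Let 45% of couples deliver in both arms and a fraction t of deliveries be twins (assumed). Newborns per couple have mean m = 0.45(1 + t) and variance 0.45(1 + 3t) − m². The chi-square assumes variance m(1 − m).

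- t = 0.10: m = 0.495. True variance 0.585 − 0.245 = 0.340, assumed 0.250, ratio 1.36. Effective cut-off 1.96/√1.36 = 1.68, so 9.3% rejections.
- t = 0.40: m = 0.63. True variance 0.990 − 0.397 = 0.593, assumed 0.233, ratio 2.54. Effective cut-off 1.96/√2.54 = 1.23, so 21.9% rejections.

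Simulation with 168 and 167 couples agrees (9.2% and 22.1%).

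**The case against.** The distortion is hypothetical. It needs two conditions, and the documents show neither. The upper figure of 25.4% takes 10 extra points of pregnancy with a loss risk five times that of control; at 30% lost it is 6.6% to 10.2%. A rejection is also not a plain false positive, because loss per pregnancy really does differ in those scenarios. What is unsupported is reading it as harm to pregnancies that would have occurred anyway. Nothing was computed separately for biochemical loss. Neither loss rate is named as primary or said to be tested. All of this stands and limits the point.

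There is also a case for keeping the loss test. With pregnancy at 50% in both arms and the same couples pregnant, it keeps its 5% error and detects 20% against 10% lost in 44.5% of trials, while the live birth test detects the resulting 40% against 45% in 14.8%. Removing the P-value would give up the more sensitive signal of harm. That stands too, so the fix labels the comparison and does not forbid it.

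It could be said that live birth was in practice counted once per delivery. The definition does not say so: its numerator is newborns.

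What survives is that both denominators follow exposure, the trial asks whether pregnancy itself changes, and the plan gives no caution.

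**Conclusion.** The point holds in a limited form. Loss per positive hCG test and loss per clinical pregnancy are conditional on events after randomisation. A difference in either is a randomised effect on loss only if the pregnant groups stay comparable in loss risk. The size is unknown; about 5% to 25% rejections is the range on the rates assumed above, and the lower end means no distortion. Separately, a chi-square on newborns per transfer cycle is not valid if there are twins. The 9% to 22% rests on the assumed delivery and twin rates, and the documents do not say how many transfers used two embryos.

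A reader might infer that the loss results are biased, that loss must not be tested, or that the live birth row settles what a loss difference means. The documents support none of these. They give no rates from which bias could be shown. The test keeps its error rate when either condition fails. At this sample size, live birth often cannot separate the explanations.

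The effect is confined to how the two loss rates and the live birth test are read. Clinical pregnancy per transfer cycle is not touched by the conditioning.

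**What to change.** 1. Compare at least one healthy living newborn, and clinical pregnancy, as one yes/no outcome per randomised couple, with risk difference, 95% CI and chi-square. Keep newborns per transfer cycle as a descriptive figure.
2. Keep both per-pregnancy loss rates, labelled as conditional on pregnancy and not a randomised comparison. Any P-value on them is exploratory and carries that label.
3. Beside them, tabulate by arm, out of all randomised couples: no pregnancy, biochemical loss, clinical loss and live birth. Give per-couple loss as a risk difference with 95% CI. Do not read it alone, because it also rises when more couples conceive.
4. State that a non-significant loss or live birth result is not evidence of no harm; the live birth interval is about plus or minus 10.7 points on the assumed rates.

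This presumes one allocation per couple. The Objective section speaks of embryos being randomised, but in the test group "the selected embryos were transferred to the combined droplet for catheter loading", which fits one medium per transfer. Nothing says each couple had a single transfer; if some had more, use the first randomised one. The documents give 335 participating couples, not the number randomised. If that number cannot be recovered, use transfer cycles and say so.

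The cost is a few table lines, one flag per couple (available if newborns are linked to couples), and a weaker claim from any loss P-value. The study period ended in December 2019, so report this as a late change to analysis and reporting, and state whether outcome data had been seen.
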